## **Background and Review of Literature:**

The long term objective of this project is to validate botulinum toxin injections as a non-inferior treatment option for pain control and ability to return to full activity for adult military members suffering from lower extremity Chronic Exertional Compartment Syndrome (CECS), when compared to surgical fasciotomy. CECS is a debilitating disorder in which pressure in muscle compartments increases with exercise and resolves with rest. This causes pain, paresthesia, and inability to tolerate exercise. CECS mainly afflicts the lower extremities, below the knee, but upper extremity CECS has also been reported. CECS mainly affects young active adults. At risk groups include males, active duty military members, and athletes, both professional and recreational. 1,3,4,5

The current standard for definitive management and treatment of CECS is surgical fasciotomy. According to a 2016 systematic review, surgical intervention for CECS is successful in only 66% of those affected, with 13% of patients reporting complications from surgery, and 6% needing a repeat procedure. Definition of success varied across studies, but included patient satisfaction, lack of surgical revision, and full return to activity. Besides risks and complications, surgery also required a mean of 13 weeks to return to full activity when effective. A 2011 Cohort showed 81% overall patient satisfaction with the procedure, but noted best results from fasciotomy were young participants <23 years old, who underwent isolated anterior compartment release. Satisfaction was defined as being pain free or significantly improved on a 5 point pain scale, varying from pain free to worse. A smaller 2014 retrospective chart review of elite athletes with CECS showed fasciotomy was initially successful in 85% with a mean return to elite activity of 10.4 weeks. However, 30.8 % had a return of symptoms within the follow-up period.

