Likewise, conservative treatment options yield mixed results. A systematic review in May of 2016 showed massage, gait changes, chemodenervation, and ultrasound-guided (USG) fascial fenestration had few adverse effects, but long term results and efficacy were unknown and unverified. Another newer therapy, minimal incision fasciotomy was effective for returning patients to previous level activity in 94% of patients after 36 months follow up in a prospective trial. Though improved final outcome from regular surgical intervention, average return to activity and return to sport was 8 and 13 weeks respectively. 

Military personnel comprise a specific patient population for whom outcomes and return to full duty is important for continued service and deployment. A 2014 military cohort found women, junior enlisted service members, and the Army soldier experienced the highest incidence of CECS. There was also an association between increasing age and CECS incidence. The study also found 78% of patients were free from medical discharge or revision after surgery at short-term to mid-term follow-up. However, 28% of service members were unable to return to full duty and 45% experienced incomplete relief of symptoms. In a similar United Kingdom military study, only 47% of subjects' symptoms improved after surgery. Additionally, a 2014 retrospective review of one United States tertiary military facility showed a return to full military duty in only 41% of patients who underwent elective fasciotomy for CECS. In that study, 78% of patients remained in the military and 71% reported satisfaction with the operative outcome.

Treatment of CECS with botulinum toxin injections has shown effective and long term relief in initial studies. An initial case series; from November 2013; showed that a single series of injections at the proximal and distal end of the affected muscle was effective in relieving pain and decreasing intramuscular pressure up to the 9 months of follow up in 94% of patients. Sixty-nine percent of those participants did have a decrease in strength, which did not affect overall motor function with treatment, but no other adverse effects. An additional 2016 case report showed effective pain and

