#### a. Interventions and Observations:

If CECS is diagnosed by intramuscular pressure (IMP) elevation, patients will be offered Botulinum toxin injection regimen into the affected compartment or referral to orthopedic surgeon for a possible surgical fasciotomy. Patients will be provided information regarding both Botulinum toxin injections and fasciotomy. Patients will be allowed to discuss fasciotomy with a surgeon prior to making a decision to participate in the study, if desired. Potential side effects of Botulinum toxin injection include possible bleeding, pain, infection, general muscle weakness, muscular atrophy, flu-like symptoms, breathing and swallowing difficulties and death. Potential side effects of fasciotomy include surgical site pain, bleeding, recurrence of symptoms, scarring, muscle weakness, nerve damage, hematoma, need for repeat operation, infection, reactions to anesthesia (e.g. anaphylaxis), blood clot, muscle wasting (atrophy), and death. These will be explained to participants during the consent discussion.

For those diagnosed with CECS and desire Botulinum toxin injections, they will receive 2 injections per affected compartment. Up to 50 units of Botulinum toxin will be injected into the proximal and distal portions of the compartment for a maximum total dose of 100 units. A solution of 100 units of Botulinum toxin per 2 mL of normal saline will be used for all injections. Standard sterile technique will be followed. Insertion in to the correct compartment will be accomplished using general landmarks. The compartment will be separated into thirds measuring from the tibial plateau to the head of the calcaneus. Injections will be given at approximately 1/3 the distance from the tibial plateau for the proximal injection and 2/3 the distance from the tibial plateau for the distal injection. If the lateral or deep posterior compartment is affected, a total of 50 units Botulinum toxin will be given, 25 units per injection. If the anterior or superficial posterior compartment is affected, a total of 100 units Botulinum toxin will be given, 50 units per injection. Of note, CECS mainly affects the anterior and lateral compartments and is rarely seen in the superficial posterior or deep posterior areas.

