For those diagnosed with CECS and desire surgical fasciotomy, the team will discuss the fasciotomy procedure and risks as mentioned above. For the procedure, the patient will be placed under general anesthesia and then linear incisions will be made into the affected compartment releasing the underlying fascial layer, reducing the pressure of the compartment. The entire procedure will be accomplished in a sterile fashion. Further details and scheduling will be per the orthopedic surgeon's recommendations.

After the initial Botulinum toxin injection regimen or fasciotomy, patients will be assessed at 1 month, 3 months, and 6 months with the LEFI and universal pain scale. Primary outcome will be pain reduction. Adequate pain reduction will be rated as less than 3 on the universal pain scale. Secondary outcomes will include return to full activity and patient satisfaction. Full activity is defined as able to run 1.5 miles and complete work duties with either no pain or pain that can be ignored. To assess patient satisfaction, patients will be asked if they were or were not satisfied with the Botulinum toxin injections at the 6 month visit.

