# **Inclusion/Exclusion Criteria:** · Adult ages 18-65 · Active duty military Unable to run 1.5 miles without producing symptoms, including aching, burning, numbness, tingling, or weakness in the affected limb Failed conservative treatment over a period of 2 months, including trial of rest, Inclusion Criteria NSAIDs, icing, and stretching routine Meets standard of care clinical diagnostic intramuscular compartment pressure criteria for CECS, based on standardized IMP needle testing. See below for testing protocol and criteria. · Prior Botulinum toxin injections into the affected limb Prior compartment release of the affected limb **Exclusion Criteria** Pregnant or becomes pregnant during the study Standard of care clinical exams indicating other more likely causes of leg pain

t. Source	r. Source of Research Material:							
Will you be using private information in this study?				□ No – Only using publically available information □ Yes –				
-	☑ protected	health informati	on (PHI)		y a covered entity			
	other type:	s of private info	rmation	Desc	cribe:			
If Yes,	research information (non-PHI) that is not publically available (i.e.,			Describe:				
	student record	ds)						
Use of iden information	itifiers with pri 1	vate						
Identifiers t	to be Used?	Column A Looked at by research team	Colum Record on enrollm log, sub list, or	ded nent oject key	Column C Recorded on data collection tool (survey, spreadsheet, etc.)	Column D Recorded on specimen containers	Column E Shared w/ others not on research team	Stored after study ended

NONE						
Names	V	V	V			
Study codes linked to individuals' identities using a key only accessible by the					_	
researcher						
Addresses						
Dates (except year)	~	✓	>			
Ages over 89						
Phone/Fax Numbers	>	~	<			
E-mails						
- SSNs	V	~	~			
- Scrambled SSNs	Specify:	Specify:	Specify:	Specify:	Specify:	Specify:
- last four of SSN	Last 4 SSN	Last 4 SSN	Last 4 SSN			
Numbers: - Medical record # - Account # - Certificate/license # - Health plan beneficiary # - Vehicle identifier/serial # - License plate #	Specify: Medical record #	Specify: Medical record #	Specify: Medical Record #	Specify:	Specify:	Specify:
- Device identifier/serial #						
Web URLs or IP addresses						
- Biometric Identifiers,						
including finger/voice prints - Full-face photo images and comparable images	Specify:	Specify:	Specify:	Specify:	Specify:	Specify:

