# **Outcome Measures:**

For the prospective portion of the study, the primary outcome will be pain reduction from either a standard of care surgical fasciotomy or an investigational Botulinum toxin treatment regimen. Adequate pain reduction will be rated as less than 3 on the universal pain scale. Secondary outcomes will include return to full activity and patient satisfaction. Full activity is defined as being able to run 1.5 miles and complete work duties with either no pain or pain that can be ignored. To assess patient satisfaction, patients will be asked if they were or were not satisfied with their surgical fasciotomy or their Botulinum toxin injections during their 6 month follow-up visit.

For the retrospective portion of the study, the same measures will be addressed for subjects who have undergone a standard of care surgical fasciotomy, but only on a pre- and post-treatment basis.

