### **Statistical Analysis:**

The primary measure to be analyzed will be comparing pre- and post-treatment pain for each of the two treatment regimens using the universal pain scale. Additionally, participants will be evaluated for return to duty, overall patient satisfaction, and the Lower Extremity Functional Index will be compared pre- and post-treatment. The study team will complete the statistical analysis.

Number of Subjects:				
	# Planned to Enroll	# Enrolled	# Planned to Complete Study	TOTAL

Number of Subjects at Scott AFB	15	0	15	15
---------------------------------	----	---	----	----

Number of Data Records Entered into the Study:					
	# Planned to Enroll	# Enrolled	# Planned to Complete Study	TOTAL	
Number of Subjects at Scott AFB	10	0	10	10	

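### Entry and 'return to full activity' use the same 1.5-mile run but different symptom lists, so an eligible patient can meet this secondary outcome before treatment

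*Combined protocol and SAP*

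**What the plan says.** Entry (Section 3, Inclusion/Exclusion Criteria) requires that the patient be "Unable to run 1.5 miles without producing symptoms, including aching, burning, numbness, tingling, or weakness in the affected limb". What matters is whether symptoms appear. No severity is set, and failure to finish the run is not required.

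The outcome appears twice in almost the same words. Section 3a has "Full activity is defined as able to run 1.5 miles and complete work duties with either no pain or pain that can be ignored". Section 6, Outcome Measures, has "Full activity is defined as being able to run 1.5 miles and complete work duties with either no pain or pain that can be ignored". It has three parts: the run, the work duties, and pain that is absent or ignorable.

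Section 6, Data Analysis, lists return to full activity among the measures followed from pre-treatment to six months. Section 6, Statistical Analysis, uses another term: "participants will be evaluated for return to duty, overall patient satisfaction". The Background describes CECS as more than pain: "This causes pain, paresthesia, and inability to tolerate exercise".

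**The concern.** The word 'return' implies that the patient was below the threshold at the start. If some patients can satisfy the definition at entry, part of the reported rate reflects who was enrolled and not what treatment did.

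Return to full activity is half of the stated hypothesis (pain reduction and ability to return to full activity) and central to the military rationale. The primary outcome is already pain. A functional outcome whose only symptom is also pain says little about the other symptoms that qualified patients for the study. With so few patients, one or two such cases would visibly move the rate.

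**Working it through.** **Inputs.** Entry criterion: Section 3, Inclusion/Exclusion Criteria. Outcome definition: Section 3a, and Section 6, Outcome Measures. Prospective sample 15 and retrospective sample 10: Section 6, Sample Size Estimation/Power Analysis. The plan gives no figure for this outcome to reproduce; its power table concerns pain below 3 only and does not depend on this point.

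**Step 1: the two rules side by side, for an untreated patient who can finish the run and the duties.**

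| Symptom on the 1.5-mile run | Meets entry symptom criterion? | Meets full activity? |
|---|---|---|
| Aching or burning, cannot be ignored | Yes | No |
| Aching or burning, can be ignored | Yes | Yes |
| Numbness, tingling or weakness only | Yes | Yes |
| None | No | Yes |

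Rows two and three meet both rules on the same day. A patient who cannot finish the run or the duties fails the outcome whatever the symptom.

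**Step 2: does anything else close the gap?** The pre-exercise and post-exercise pressure test uses a treadmill run to intolerance, but no distance is set, so it does not show failure at 1.5 miles. No text requires patients to fail the full-activity definition before treatment. Data Analysis includes a pre-treatment time point but gives no rule for patients who already qualify. Neither the list of clinical data in Section 3 nor the procedures table names an item that records full activity. The survey forms are listed only as attachments, so their content cannot be checked here.

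**Step 3: size.** The share of patients in rows two and three is not given. The values below are assumptions. If k of the 15 prospective patients meet the definition at entry and are scored as returned, they contribute k/15 to the pooled rate:

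- k = 1: 1/15 = 6.7 points
- k = 2: 2/15 = 13.3 points
- k = 3: 3/15 = 20.0 points

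If each patient has probability f of being in the overlap, the chance of at least one in 15 is 1 − (1 − f)^15: 54% for f = 5%, 79% for f = 10%, and 96% for f = 20%.

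The distortion relative to leaving these patients out is smaller. If the remaining patients return at rate q and the overlap share is w, the reported rate is q + (1 − q)w. For illustration, q is taken from two surgical figures in the Background: 41% returned to full military duty in one review, and 28% were unable to in another cohort (so 72% were able). With w = 20%:

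- q = 41%: 0.41 + 0.59 × 0.20 = 52.8%, a rise of 11.8 points
- q = 72%: 0.72 + 0.28 × 0.20 = 77.6%, a rise of 5.6 points

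**Step 4: arms.** Section 3 describes two prospective arms but gives 15 as one total. If the 15 were split 8 and 7 (an assumption), one such patient would be 1/8 = 12.5 or 1/7 = 14.3 points of an arm's rate. In the retrospective group each would be 1/10 = 10 points.

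**The case against.** The strongest reply is that the overlap may be nearly empty. Eligible patients have failed two months of conservative care, meet the pressure criteria and are choosing between injection and surgery. The Background describes people who cannot tolerate exercise. Aching and burning are also forms of pain, so the wholly uncounted symptoms are three, not five. This stands as a reason to expect small numbers. It does not remove the overlap, because neither rule excludes it.

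It is also fair to say that entry criteria may be broad for diagnosis while an outcome measures function, and that the LEFI and satisfaction cover some of the same ground. But the LEFI is not part of the full-activity definition, and neither measure settles who was already at full activity.

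Three stronger readings are tempting and are not supported.

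- **That the outcome ignores weakness.** It does not. Weakness or numbness that stops the run or the duties counts as failure. Only a deficit that stops neither is missed.
- **That the gap favours injection.** A reader might infer this from the toxin risks, which include "general muscle weakness, muscular atrophy, flu-like symptoms, breathing and swallowing difficulties and death", and from the cited injection series. But the series reports: "Sixty-nine percent of those participants did have a decrease in strength, which did not affect overall motor function with treatment". That is not evidence of weakness felt on a run. Muscle weakness, nerve damage and atrophy are listed for fasciotomy too, the same definition applies to both groups, and no weakness rate after fasciotomy is given.
- **That Statistical Analysis replaces the outcome with one that has no run.** The same section names and defines return to full activity, so 'return to duty' reads as loose wording for it. The terms should match, but a second endpoint is not shown.

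**Conclusion.** The point holds as a gap in definition and baseline recording. An eligible patient who can finish 1.5 miles and work duties with numbness, tingling, weakness or ignorable aching meets the outcome before treatment, and the plan does not say how to handle that patient.

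The size is unknown. The 0 to 20 point range rests on two assumptions: that 0 to 3 of the 15 prospective patients are affected, and that all 15 are pooled. The documents do not show that such patients are common, nor which treatment group would gain. The outcome is secondary and the sample-size table does not use it. This is a cheap improvement.

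**What to change.** 1. In Section 3a and in Outcome Measures, keep the run and the duties, and apply the existing threshold (none, or can be ignored) to all five entry symptoms: aching, burning, numbness, tingling and weakness.
2. Record full-activity status before treatment with the same item used at follow-up; in the retrospective group, obtain it by recall. If an attached form already carries the item, cite it.
3. Count return only in patients who did not meet the definition before treatment, and report by group how many did. This step is needed as well as the first, because a patient with ignorable symptoms would still meet the revised definition at entry.
4. In Statistical Analysis, use 'return to full activity' in place of 'return to duty'.

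The cost is one extra survey item, more recall for the retrospective group, a slightly smaller denominator (12 instead of 15 if three patients already qualify) and possibly a lower return rate. Treatment and visits do not change.

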#### b. Setting:

The study will be carried out in the 375 MDOS outpatient O'Fallon Family Medicine Residency Clinic located at 3 St. Elizabeth's Blvd, Suite 4000, O'Fallon, ILThe clinic is also part of a family medicine residency program. All counseling, injections, and follow-up will be done in the family medicine clinic. All standard of care tests for prescreening of subjects will be performed at the Scott Air Force Base medical group radiology and laboratory facilities. These tests include blood tests, X-rays, physical exam and intramuscular compartment pressure readings.

# c. Date(s):

For the prospective portion of the study for patients receiving Botulinum toxin injections, expected timeframe for data collection is April 2017 through April 2020.

For the retrospective portion of the study, we will review medical results and pain assessments from patients who had a surgical fasciotomy during the time period of July 1, 2016 through June 30, 2017.

#### d. Subjects:

Patients will be active duty military adults, 18 years of age or older, who have clinical signs and symptoms of chronic exertional compartment syndrome in any muscular compartment of the lower leg. All patients referred to the sports medicine clinic for leg pain will be screened for possible inclusion into the study, following standard of care clinical tests. After an initial standard of care evaluation, if CECS is suspected, each subject will be asked to participate in the study and will be formally consented by a member of the research team.

Other exertional causes of leg pain will be ruled out by a standard of care clinical examination (general, orthopedic, neurologic, and functional) and supporting workup. This will include plain radiographs of the knee, tibia, fibula, and ankle on the affected side of the lower extremity. Any patient with an abnormal finding not consistent with CECS, such as a stress fracture, will be ruled out from participating in the research study. Patients will have tried conservative treatment for at least 2 months prior to compartment testing to include rest, stretching, ice, and NSAIDs. All patients reporting lower extremity pain will be examined by a physician on the study team to confirm CECS under the direct supervision of [name].

Intramuscular pressure in lower leg compartments will be obtained by IMP needle insertion (standard of care) into all four compartments of both lower legs before and after exercise. Infection risk will be decreased by sterilizing the puncture site with chlorhexidine swabs. Pain will be decreased by injecting 0.5 mL of 1% lidocaine with epinephrine superficially to anesthetize the skin. Pressure will be transmitted to a pressure transducer for measurement in mm Hg. The exercise portion will be standardized by having patients run on the same treadmill with enough speed until their symptoms begin. After symptoms begin, the patient will be asked to continue running until he or she cannot tolerate, at which time the exercise will be stopped and the patient will lie supine for repeat intramuscular pressure measurements. Definitive diagnosis of CECS will be based on intramuscular pressure elevations according to Pedowitz et al. This includes 1) a pre-exercise pressure greater than or equal to 15 mm Hg and 2) a 1-5 minute post-exercise pressure of greater than or equal to 30 mm HG.

# **Inclusion/Exclusion Criteria:** · Adult ages 18-65 · Active duty military Unable to run 1.5 miles without producing symptoms, including aching, burning, numbness, tingling, or weakness in the affected limb Failed conservative treatment over a period of 2 months, including trial of rest, Inclusion Criteria NSAIDs, icing, and stretching routine Meets standard of care clinical diagnostic intramuscular compartment pressure criteria for CECS, based on standardized IMP needle testing. See below for testing protocol and criteria. · Prior Botulinum toxin injections into the affected limb Prior compartment release of the affected limb **Exclusion Criteria** Pregnant or becomes pregnant during the study Standard of care clinical exams indicating other more likely causes of leg pain

t. Source	r. Source of Research Material:							
Will you be using private information in this study?				□ No – Only using publically available information □ Yes –				
-	☑ protected	health informati	on (PHI)		y a covered entity			
	other type:	s of private info	rmation	Desc	cribe:			
If Yes,	research information (non-PHI) that is not publically available (i.e.,			Describe:				
	student record	ds)						
Use of iden information	itifiers with pri 1	vate						
Identifiers t	to be Used?	Column A Looked at by research team	Colum Record on enrollm log, sub list, or	ded nent oject key	Column C Recorded on data collection tool (survey, spreadsheet, etc.)	Column D Recorded on specimen containers	Column E Shared w/ others not on research team	Stored after study ended

NONE						
Names	V	V	V			
Study codes linked to individuals' identities using a key only accessible by the					_	
researcher						
Addresses						
Dates (except year)	~	✓	>			
Ages over 89						
Phone/Fax Numbers	>	~	<			
E-mails						
- SSNs	V	~	~			
- Scrambled SSNs	Specify:	Specify:	Specify:	Specify:	Specify:	Specify:
- last four of SSN	Last 4 SSN	Last 4 SSN	Last 4 SSN			
Numbers: - Medical record # - Account # - Certificate/license # - Health plan beneficiary # - Vehicle identifier/serial # - License plate #	Specify: Medical record #	Specify: Medical record #	Specify: Medical Record #	Specify:	Specify:	Specify:
- Device identifier/serial #						
Web URLs or IP addresses						
- Biometric Identifiers,						
including finger/voice prints - Full-face photo images and comparable images	Specify:	Specify:	Specify:	Specify:	Specify:	Specify:
Any other pre-existing unique identifying number, characteristic, or code						
Coding Plan?						
Describe the method that we be used to create and assi unique study codes to date	ign					
Describe the method that we be used to create and assi unique study codes to specimens.	gn N/A,	✓ N/A, not collecting specimens  Describe:				
What is the format of the key?						
Who will have access to the key?	, ,	ncipal investiga				
Where will the key be store and how will it be protected	ed drawer. d? Confide	ntiality measure	Il be stored in princes: All electronic inf	ormation will be		
Complete the table.	network	with a double p	assword protected	acument		

Source of Research Material per Participant	# Routine	# Research	# Total
(Procedures)	Care	Driven	Procedures
X-rays, blood samples	1	0	1
Intramuscular compartment pressure readings	1	0	1
Lower extremity functional index	1	3	4
Universal Pain Scale	1	3	4
Satisfaction survey	0	1	1
Urine Pregnancy Test	0	1	1

